9.1.8 Acquisition of Sputum

Sputum (approximately 1.3-2.0 grams) will be obtained at Visit 2 (Day 1) prior to the infusion of stem cells and on Visits 3 (Day 7) and 5 (Day 28) via spontaneous expectoration. Sputum samples will be split according to priority for analyses. The first aliquot will be sent to the microbiology laboratory at University Hospitals Cleveland Medical Center where quantitative bacteriology will be performed, and the second aliquot will be processed and saved for research studies. Sputum will be processed according to the current standard operating procedure (SOP) developed by CF Foundation's Therapeutics Development Network. Subjects unable to spontaneously expectorate sputum will undergo sputum induction according to the current SOP developed by CF Foundation's Therapeutics Development Network. If a sputum sample cannot be produced, or the quantity of the sample is not sufficient for all the tests to be performed, this is not considered a deviation.

9.1.9 Intravenous Infusion of hMSCs

Fresh MSCs are infused at Visit 2 (Day 1) from a syringe into a venous catheter followed by a saline wash. After the infusion of cells is complete, 10-ml of a normal saline flush is given immediately and a running IV of normal saline is maintained at 250 ml/hr for 4 hours. Subjects are monitored for 24 hours for infusion-related toxicity. Temperature, blood pressure, heart rate, respiratory rate and oxygen-saturation are measured prior to infusion and at 10 (\pm 5), 20 (\pm 5), 30 (\pm 5), 60 (\pm 15), and 90 (\pm 15) minutes and 2 hours (\pm 15 minutes) and 4 (\pm 15 minutes) hours post-infusion and then every 4 (\pm 15 minutes) hours for the remainder of the 24-hour observation period. Any toxicity is treated at the discretion of the managing physician, and toxicities are reported to the Principal Investigator, IRB, and FDA as appropriate.

MSC infusion has been very well tolerated. Although theoretically of concern, there have been no reported cases of immunosuppression, autoimmunity, cancer, significant lung damage, severe infection, or clinically significant ectopic tissue formation attributable to MSC infusion. MSC infusion could cause infection if the cells are contaminated. Strict aseptic technique during bone marrow aspiration, culture, thawing, and infusion and stringent microbiologic screening minimize this risk. Because of the immunosuppressive effects of MSCs, recipients potentially are at increased risk for infection.

9.1.10 Bone Marrow Exam

Healthy volunteers who meet screening criteria and who consent to having their mesenchymal stem cells subsequently infused into study subjects with CF will undergo a bone marrow examination according to SOPs developed by the CCC well in advance of the infusion. Either a unilateral or bilateral (depending on the yield of bone marrow aspirate) posterior iliac crest bone marrow aspiration will be performed using local anesthetics 1% Xylocaine (approximately 10 ml intradermal and subcutaneous), preservative-free bupivacaine 0.25% (approximately 10-20 ml injected locally to the site), morphine sulfate (approximately 2-6 mg by IV). Lorazepam (1 mg oral or IV) may be used if needed. Approximately 60-80 ml of marrow is pulled into syringes containing preservative-free heparin (400 units/25cc marrow) using a few brisk pulls. Bone marrow samples will be processed, and MSCs will be prepared according to CCC SOPs as previously described.

If a subject with CF consents to undergoing the optional bone marrow exam, screening procedures will be performed at Visit 1 and a single bone marrow aspiration of the posterior iliac crest will be performed at Visit 1A under local anesthetic 1% Xylocaine (approximately 10 ml intradermal and subcutaneous). For CF subjects, the optional bone marrow aspiration procedure (Visit 1A) must be completed at least 14 days before Day 1 (Visit 2). Preservative-free bupivacaine 0.25% (approximately 10-20 ml injected locally to the site), morphine sulfate (approximately 2-6 mg by IV), and lorazepam (1 mg oral or IV) may be used if needed. Approximately 5-20 ml of marrow is pulled into a syringe containing preservative-free heparin (400 units/25cc

marrow) using a brisk pull. MSCs isolated from subjects with CF will be evaluated in pre-clinical models to determine how they differ from donor MSCs. The CCC and NCRM at Case Western Reserve University have emerging cell therapy assay methods so that BM samples from subjects with CF are able to be archived and used at a later time to more fully characterize the CF defect.

The risks of a bone marrow aspiration include pain at the time of the aspirate, which is common but well controlled with adequate use of Xylocaine, bupivacaine and morphine. Other risks include bleeding, infection at the site of the aspirate, and occasional lightheadedness or fainting due to a vasovagal reaction after the procedure. Healthy volunteers and subjects with CF, who undergo the optional bone marrow examination, will be followed by the study PI or designee for AEs related to the procedure.

Inclusion Criteria for Healthy Volunteer Donors:

- 1) Male/female age \geq 18 years
- 2) Able to understand and sign ICF (a legally authorized representative will not be permitted)

Inclusion Criteria for CF Donors:

- 1) CF subject enrolled in the main study and consented to this optional procedure

Exclusion Criteria for both Healthy Volunteer Donors and CF Donors:

- 1) Fever or current illness on the day of the cell collection
- 2) Evidence of communicable disease.
- 3) Any significant change in health status within 2 weeks prior to cell collection that the PI/Sub-Investigator deems relevant to exclude participation
- 4) Subject-reported history of organ transplantation
- 5) Subject-reported history of HIV, hepatitis B or C, or syphilis
- 6) For HV donors only, subject-reported known history of being diagnosed with cystic fibrosis (CF) or being a CF carrier (one copy of CF gene mutation)
- 7) Positive screening blood test result for any infectious disease.
- 8) For HV donors only, positive test result for CMV or a CF gene mutation.
- 9) Pregnant, planning a pregnancy, or breast-feeding at screening.

9.1.11 Adverse Events

Information regarding occurrence of AEs will be captured throughout the study from the time of consent until Telephone Call 4 (Month 12 \pm 1). Duration (start and stop dates), severity/grade, outcome, treatment and relation to investigational product or study procedures will be recorded in the CRF.

9.2 Clinical Laboratory Measurements

9.2.1 Hematology

Blood (5 ml) will be obtained at all study visits and sent to the clinical hematology laboratory at University Hospitals Cleveland Medical Center for a complete blood count (hemoglobin, hematocrit, red blood cell count, white blood cell count, white blood cell differential, and platelet count), ESR, and serum hs-CRP determinations for assessment of systemic evidence for infection and/or inflammation.

9.2.2 Blood Chemistry Profile

Blood (5 ml) will be obtained at all study visits and sent to the clinical chemistry laboratory at University Hospitals Cleveland Medical Center for determination of sodium, potassium, chloride, bicarbonate, random glucose, BUN, creatinine, aspartate aminotransferase (AST/SGOT), alanine aminotransferase (ALT/SGPT), alkaline phosphatase, total bilirubin, direct bilirubin, albumin and LDH. Because vitamin D may influence hMSC function, a vitamin D concentration will be obtained at Visit 2 and analyzed *post hoc*.

9.2.3 Pregnancy Test

A pregnancy test will be performed on female subjects who are of childbearing potential prior to their participation in the study. A serum pregnancy test will be done at screening (blood volume is included in the sample collected for chemistry profile) and urine pregnancy tests will be done at Visits 2, 5 and early termination.

9.2.4 Urinalysis

Urine will be obtained at all study visits and sent to the clinical laboratory at University Hospitals Cleveland Medical Center for determination of color, specific gravity, pH, protein, glucose, ketones, and blood.

9.3 Research Assessments

9.3.1 Serum Measurements of Inflammatory Mediators

40-mL of whole blood will be collected and placed in serum separator tubes at Visits 2 (Day 1), 3 (Day 7), and 5 (Day 28). Samples will be centrifuged. The serum will be removed, aliquoted, and frozen at -80°C. Specimens will be batched and analyzed for calprotectin, MPO, GM-CSF, IL-1 β , IL-6, IL8, IL-17, and TNF- α in the Bioanalyte Core of the CF Research Center at Case Western Reserve University.

9.3.2 Sputum Cell Count and Differential

Sputum (approximately 0.065 gm) will be collected at Visits 2 (Day 1), 3 (Day 7), and 5 (Day 28) for determination of white cell counts (by hand counting) and differential cell counts performed by the CF-Therapeutics Development Network (TDN) Center for Interpretive Cytology at Case Western Reserve University according to the current CF-TDN SOP.

9.3.3 Sputum Cytokine Measurements

Sputum (approximately 0.75 gm) for determination of IL-1 β , IL-6, IL-8, IL-10, IL-17, GM-CSF, MIP-3 α , TNF- α , neutrophil elastase, α_1 -anti-trypsin, and MMP-9 will be collected at Visits 2 (Day 1), 3 (Day 7), and 5 (Day 28). Specimens will be collected in a sterile specimen cups. Sputum will be processed according to the current CF-TDN SOP. Aliquots will be batched and analyzed in the Bioanalyte Core of the CF Research Center at Case Western Reserve University.

9.3.4 Quantitative Bacteriology

Sputum (approximately 0.5 gm) will be collected at Visits 2 (Day 1), 3 (Day 7), and 5 (Day 28) for culture. All sputum specimens will be collected in a sterile specimen cup, Quantitative culture for typical CF pathogens will be performed in the clinical microbiology laboratory at University Hospitals Cleveland Medical Center.

9.3.5 Respiratory and Systemic Symptoms Questionnaire (RSSQ)

Investigators or their designee will interview each subject to complete an RSSQ (Boehringer Ingelheim), which is designed to capture signs and symptoms, at each study visit and for any other encounter for increased respiratory symptoms. Such encounters may occur between study visits and include unscheduled visits and phone encounters. The RSSQ must be completed prior to any other study procedures.

9.3.6 Cystic Fibrosis Respiratory Symptom Diary (CFRSD)

Study participants will complete the CFRSD (University of Washington) five times, at Visits 2-5 and once at home between Visits 4 and 5. The CFRSD will also be completed if the subject has an acute illness visit between Visit 2 and Visit 5. The CFRSD is designed to capture a change in symptoms and to quantify their severity and magnitude for the previous 24 hours during periods of stability, medically treated pulmonary exacerbations, and recovery from pulmonary exacerbations. The CFRSD will be reviewed at Visits 2-5, during Phone Call #2, and at any applicable Acute Illness Visit/Early Termination Visit. The CFRSD may be reviewed after the RSSQ is performed but must be reviewed prior to any other study procedures.

9.4 Screening Assessments for Bone Marrow Collection

9.4.1 Donor History Questionnaire (DHQ) for Healthy Volunteers Participating in the Bone Marrow Collection

The DHQ and its related materials (e.g., Medication Deferral List, Donor Educational Materials) will be used as a tool to screen donors for communicable disease risk factors. The DHQ and related documents will be obtained from the American Association of Blood Banks (AABB) website.

9.4.2 Measurements of Infectious Disease Markers for Healthy Volunteers Participating in the Bone Marrow Collection

Blood (28ml) will be obtained and sent to the Indiana Blood Center for determination of the following infectious disease markers: hepatitis B surface antigen (HBsAg), hepatitis C virus (HCV), human immunodeficiency virus (HIV1,2), hepatitis B core antibody (HBcore), human T-cell lymphotropic virus types I and II (HTLV1/II), blood group and Rh antigen (ABORh), antibody screen (AbScr), Treponema pallidum; cytomegalovirus (CMV), HIV nucleic acid test (HIVNAT), hepatitis C nucleic acid test (HCVNAT), West Nile Virus nucleic acid test (WNVNAT), and Chagas. Any positive result will be reported to the subject (verbally and in writing) and to any local medical agencies as required by law, and the subject will be instructed to follow-up with a primary care physician or will be provided a referral to an appropriate physician. Bone marrow collection will occur within 7 days of communicable disease testing, per FDA guidelines stipulated in 21CFR.1271.80(b).

9.4.3 Cystic Fibrosis Genetic Screening for Healthy Volunteers Participating in the Bone Marrow Collection

Blood (2-4ml) will be obtained and sent to the Center for Human Genetics Laboratory of University Hospitals Cleveland Medical Center to determine the carrier status of an individual for the most common 41 mutations in the CFTR gene associated with cystic fibrosis. Any positive results will be reported to the subject and genetic counseling will be provided.

9.4.4 Measurements of Infectious Disease Markers for CF Subjects Participating in the Optional Bone Marrow Collection

Blood (10 ml) will be obtained and sent to the University Hospitals Cleveland Medical Center Laboratory for determination of the following infectious disease markers: hepatitis B and C, syphilis and HIV. Any positive result will be reported to the subject (verbally and in writing) and to any local medical agencies as required by law, and the subject will be instructed to follow-up with a primary care physician or will be provided a referral to an appropriate physician.

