10.2 Visit 1A (if applicable, Optional Bone Marrow Aspiration) (Day -35 to -14)

1. Perform and record vital signs, including a blood pressure after the subject has been seated for 5 minutes
2. Review and record interval history
3. Review and record any changes to concomitant medications
4. Perform urine pregnancy test if applicable
5. Perform an abbreviated physical exam
6. Review inclusion/exclusion criteria
7. Perform bone marrow aspiration
8. Subject to rest for 30 minutes post-procedure
9. Record any AEs that may have occurred during the study visit

10.3 Follow-up Phone Call (if applicable, 24 (\pm 12) hours after Optional Bone Marrow Aspiration)

1. Review and record interval history
2. Review and record any changes to concomitant medications
3. Record any AEs that may have occurred since bone marrow aspiration

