10.15 Acute Illness/Early Termination Visit

1. Review and record RSSQ prior to any other study procedures
2. If Acute Illness or Early Termination Visit occurs before Visit 5, administer and review CFRSD prior to any other study procedures and record any AEs that occurred since last Visit or Telephone call
3. Review and record interval history
4. Review and record any changes to concomitant medications
5. Measure and record weight without shoes
6. Perform and record vital signs, including a blood pressure after the subject has been seated for 5 minutes
7. Perform and record oximetry
8. Perform a complete physical examination
9. Collect blood for clinical laboratory tests (comprehensive chemistry panel, ESR, hs-CRP, complete blood count with differential, direct bilirubin and LDH)
10. Collect urine for clinical laboratory test (urinalysis)
11. Collect urine for pregnancy test
12. Administer 3 puffs of albuterol 15 minutes prior to spirometry if subject performed a sputum induction during the study
13. Perform and record spirometry
14. Record any AEs that may have occurred during the study visit

For Healthy Volunteer Subjects:**10.16 Visit 1 (Screening Visit: Day -30 to -7)**

1. Review the study with the subject and obtain written informed consent and HIPAA authorization
2. Assign the subject a unique screening number
3. Record demographics and other baseline data
4. Record medical and surgical history
5. Record concomitant medications
6. Review inclusion/exclusion criteria
7. Perform and record vital signs, including a blood pressure after the subject has been seated for 5 minutes
8. Complete Donor History Questionnaire (DHQ)

9. Collect 32 ml blood for laboratory tests (infectious disease markers, CMV, CF mutations). Collect 2 ml blood for serum pregnancy test if applicable.
10. Record any AEs that may have occurred during the study visit from the time of consent

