10.17 Visit 2 (Bone Marrow Aspiration)

1. Perform and record vital signs, including a blood pressure after the subject has been seated for 5 minutes
2. Review and record interval history
3. Review and record any changes to concomitant medications
4. Perform urine pregnancy test if applicable
5. Perform an abbreviated physical exam
6. Review inclusion/exclusion criteria
7. Perform bone marrow aspiration
8. Subject to rest for 30 minutes post-procedure
9. Record any AEs that may have occurred during the study visit

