APPENDIX IIa. SCHEDULE OF STUDY VISITS FOR OPTIONAL STEM CELL COLLECTION FROM CF SUBJECT DONORS

	Visit 1 Screening	Visit 1A	Follow-up Phone Call
	Day -42 to -10¹	Day -35 to -14	24 (\pm 12) hours after bone marrow aspiration
Informed consent	X		
Interval history		X	X
Review previous and concomitant therapy		X	X
Review inclusion/exclusion criteria	X	X	
Phlebotomy for infectious disease limited panel	X		
Vital signs		X	
Urine pregnancy test (if applicable)		X	
Abbreviated physical exam		X	
Bone marrow aspiration of the posterior iliac crest		X	
Adverse events	X	X	X

¹The Visit 1 Screening window in this table refers to the main study (for consistency with the table in Appendix II). If a CF subject plans to participate in the optional stem cell collection procedure at Visit 1A, then the Visit 1 Screening must be completed by Day -14 or earlier in order to complete Visit 1A and Visit 1 at the appropriate times.

**APPENDIX IIb. SCHEDULE OF STUDY VISITS FOR STEM CELL COLLECTION FROM
HEALTHY VOLUNTEER DONORS**

	Visit 1 Screening	Visit 2	Follow-up Phone Call
	Day -30 to -7	Day 1	24 (\pm 12) hours after bone marrow aspiration
Informed consent	X		
Medical & surgical history	X		
Demographics and baseline characteristics	X		
Interval history		X	X
Review previous and concomitant therapy	X	X	X
Review inclusion/exclusion criteria	X	X	
DHQ	X		
Serum pregnancy test	X		
Phlebotomy for infectious disease panel including CMV	X		
Phlebotomy for CF mutation screening	X		
Vital signs	X	X	
Urine pregnancy test (if applicable)		X	
Abbreviated physical exam		X	
Bone marrow aspiration of the posterior iliac crest		X	
Adverse events	X	X	X

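### The healthy-donor screening window (Day -30 to -7) was not narrowed to Section 9.4.2's 7-day limit between infectious-disease testing and marrow collection; counted from the draw, at most one of 24 permitted days complies

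*Combined protocol and SAP*

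**What the plan says.** Section 9.4.2 sets the limit for healthy volunteers: "Bone marrow collection will occur within 7 days of communicable disease testing". It gives a federal regulation as the source. The same section has 28 ml of blood "sent to the Indiana Blood Center for determination of the following infectious disease markers", so the assay is done off site. It does not say whether the 7 days start at the draw or at the assay.

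The visit schedule is set elsewhere:

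- Section 10.16 is headed "Visit 1 (Screening Visit: Day -30 to -7"), and its item 9 reads "Collect 32 ml blood for laboratory tests (infectious disease markers, CMV, CF mutations").
- Appendix IIb marks the row "Phlebotomy for infectious disease panel including CMV" at Visit 1 only. It marks the aspiration at Visit 2, in a column headed Day 1.
- Section 10.17, the aspiration visit, includes one laboratory test, "Perform urine pregnancy test if applicable", and no blood draw. Its item 6 is a review of the inclusion and exclusion criteria.

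Section 9.1.10 excludes a donor with a positive infectious-disease screening result. For CF donors, footnote 1 to Appendix IIa narrows the Visit 1 window so that it fits the timing of Visit 1A. Appendix IIb has no comparable footnote for healthy donors.

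**The concern.** Staff schedule visits from Section 10 and the Appendix II tables. A coordinator who books a healthy donor inside the printed window can comply fully with Section 10.16 and Appendix IIb and still miss the interval in Section 9.4.2. Nothing in the schedule flags the 7-day limit, and no later draw would repair a miss.

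Few people are donors, but their cells go to many. Section 4.1 foresees one or two healthy donors, and Section 1.3.5 plans one donor preparation for all infusions. One late interval could therefore attach to the cells given to up to 15 recipients. The tests on expanded cells before release, listed in Section 1.3.7, do not name the donor infectious-disease panel, so they are not shown to replace it. What is at stake is a deviation from the protocol's own donor-testing interval.

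**Working it through.** **Inputs**

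- Limit: 7 days (Section 9.4.2).
- Permitted draw days: Day -30 to Day -7 (Section 10.16, Appendix IIb).
- Aspiration: Day 1 (Appendix IIb).
- Repeat draw: none (Section 10.17, Appendix IIb).

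**Is the Visit 1 draw the one that Section 9.4.2 means?** Section 9.4.2 asks for 28 ml and Section 9.4.3 (CFTR screening) for 2-4 ml. The sum is 30-32 ml, which matches the 32 ml in Section 10.16 item 9. The panel is in that draw.

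**Size of the window.** 30 - 7 + 1 = 24 days.

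**Day count.** The protocol does not state whether there is a Day 0. Section 6.1 describes main-study screening as lasting 10 to 42 days, and the window in Section 10.1 is Day -42 to -10. Without a Day 0, Day -42 is 42 days before Day 1 and Day -10 is 10 days before it, which matches. With a Day 0 the figures would be 43 and 11. The CF-donor timing does not settle the question. Section 9.1.10 says the optional aspiration "must be completed at least 14 days before Day 1 (Visit 2"), and Section 10.2 is headed "Visit 1A (if applicable, Optional Bone Marrow Aspiration) (Day -35 to -14"). Day -14 is 14 days before Day 1 without a Day 0 and 15 days with one, and both satisfy that minimum.

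**Interval from draw on Day -d to aspiration on Day 1.** Without a Day 0 it is d days. With a Day 0 it is d + 1 days. Here d runs from 7 to 30.

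| Count from the draw | Shortest | Longest | 7 days or less | Over 7 days |
|---|---|---|---|---|
| No Day 0 | 7 | 30 | 1 (Day -7) | 23 of 24 (95.8%) |
| With Day 0 | 8 | 31 | 0 | 24 of 24 |

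Without a Day 0, the 23 days exceed the limit by 8 - 7 = 1 day up to 30 - 7 = 23 days.

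**Interval from the assay.** If the assay is done L days after the draw, the interval is d - L (no Day 0). The protocol gives no value for L and does not say that it is constant, so the number of complying days cannot be calculated.

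**The case against.** The strongest reply is that the two provisions do not contradict each other. A broad visit window and a specific binding limit can be followed together: draw on Day -7 and aspirate on Day 1. A deviation arises only if staff overlook Section 9.4.2. This stands in part. Without a Day 0, one day satisfies both, so it would be wrong to call them irreconcilable. But a schedule that permits 24 days, of which one fits the rule, leaves compliance to memory. Appendix IIa shows that the protocol can handle such a timing problem with a footnote.

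A second reply is that *testing* may mean the assay. That also stands as a possibility, since the blood is sent out. A reader might still infer that most of the window must fail even then. For one fixed lag, d - L has to lie between 0 and 7, because the result must precede aspiration. That allows at most 8 draw days and leaves 24 - 8 = 16 failing. The documents do not support this inference, because nothing fixes the lag. With a variable lag, a draw on Day -20 assayed on Day -5 gives an interval of 5 days and complies.

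A third reply is that the consequence is small. This stands. The donor questionnaire, the exclusions for communicable disease and for illness on the collection day, and the criteria review at Visit 2 all remain. Collection takes place well ahead of infusion, so a late interval could be noticed before any dosing.

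Finally, the text of the cited regulation is not in the documents. Whether the 7-day sentence or the visit window should give way cannot be decided from the protocol alone.

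**Conclusion.** The mismatch is real and lies between current sections. Counted from the draw, 23 of 24 permitted days exceed the limit without a Day 0, and all 24 exceed it with one. The finding therefore does not depend on the day-count convention, though whether Day -7 complies does. It does depend on starting the clock at the draw, and no figure can be given for the assay reading.

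The 96% is a share of calendar days. A reader might take it as a probability of deviation or as a risk to recipients. The documents support neither: they do not say how draw days are chosen within the window, and they show no route to harm beyond an older test date.

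This is a visit window that was not narrowed to the protocol's own rule. It concerns one or two donors and touches no endpoint, sample size or analysis. Severity is minor.

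**What to change.** 1. Check the 7-day sentence in Section 9.4.2 against the regulation it cites.
2. If the limit stands, add a footnote to Appendix IIb, on the model of Appendix IIa footnote 1, and amend the Section 10.16 heading and item 9. The donor infectious-disease panel should be drawn no more than 7 days before aspiration, with results back before the criteria review in Section 10.17 item 6.
3. State in Section 9.4.2 whether the 7 days run from the draw or from the assay.

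The cost is a tighter screening window for one or two donors. If the clock starts at the draw and the laboratory needs T days (not given; an assumption), the usable draw days run from Day -7 to Day -T without a Day 0, which is 8 - T days: 6 if T = 2, 3 if T = 5, 1 if T = 7, and none if T is above 7. The laboratory's turnaround should therefore be confirmed before the text is changed. If the whole of Visit 1 moves, the CFTR result must also be back in that time. No extra visit is needed, and CF subjects and the analysis are unaffected.
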